Subjects will have clinic visits and procedures as outlined in Table 2. Telephone calls to the subjects will be made on the first 2 days after a dose adjustment. An unscheduled visit will be made as early as

possible for dose adjustments or evaluation of safety/tolerability issues. Efforts will be made to ensure that the subject's caregiver remains the same for all study visits. All post-Baseline clinic visits will have a window of ± 2 days relative to the date of the Baseline visit (Visit 3).

Subjects randomized to SEP-363856 will receive flexible doses of SEP-363856 (25, 50, or 75 mg/day). Subjects will receive SEP-363856 25 mg/day for 1 week (Days 1 - 7). If there are no safety or tolerability issues subjects should be up- titrated to 50 mg/day at Visit 4 (Week 2). Subjects still receiving SEP-363856 25 mg/day must have their dose up- titrated to 50 mg/day at Visit 5 (Week 3), unless approved to stay at 25 mg/day by Medical Monitor due to safety and tolerability concerns. At the investigator's discretion, subject may up -titrate to 75 mg during scheduled visits. During the double-blind period, up-titration will not be allowed after Visit 6 (Week 5). Dose reductions to 50 mg/day or 25 mg/day will be allowed by 1 dose level, at any time for reasons of safety and tolerability. During the double-blind period, following a dose reduction, subjects may increase their dose to the next dose level up to Visit 6 (Week 5) at the Investigator's discretion and only during scheduled visits. If safety or tolerability issues result in study dose discontinuation or reduction, the Investigator must contact the Medical Monitor before the subject is rechallenged. The study medication can be re-introduced if agreed to by the Investigator and Medical Monitor.

Dosing Schematic

Notes:

- Dose reduction is allowed at any time for reasons of safety or tolerability; during unscheduled or scheduled visits.
- During the Double-Blind Period, up-titration to a prior dose level is allowed at Investigator's discretion and only during a scheduled visit.
- At Visit 5 (Week 3), the dose should be up titrated to 50mg/day. In the event of tolerability/safety concerns, the dose may remain at 25 mg/day with Medical Monitor approval.
- Visit 6 (Week 5) is the last visit where up-titration can occur during the Double-Blind Period.

Open-label Extension Period:

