Subjects randomized to SEP-363856 will receive flexible doses of SEP-363856 (25, 50, or 75 mg/day). Subjects will receive SEP-363856 25 mg/day for 1 week (Days 1 - 7). If there are no safety or tolerability issues, subjects should be up-titrated to 50 mg/day at Visit 4 (Week 2). Subjects still receiving SEP-363856 25 mg/day must have their dose up-titrated to 50 mg/day at Visit 5 (Week 3), unless approved to stay at 25 mg/day by the Medical Monitor due to safety and tolerability concerns. At the investigator's discretion, subject may up-titrate to 75 mg during scheduled visits. During the double-blind period up-titration will not be allowed after Visit 6 (Week 5). Dose reductions to 50 mg/day or 25 mg/day will be allowed by 1 dose level, at any

time for reasons of safety and tolerability. During the double-blind period, following a dose reduction, subjects may increase their dose to the next dose level up to Visit 6 (Week 5) at the Investigator's discretion and only during scheduled visits. If safety or tolerability issues result in study medication dose discontinuation or reduction, the Investigator must contact the Medical Monitor before the subject is rechallenged. The study medication can be re-introduced if agreed to by the Investigator and Medical Monitor.

Figure 2: Dosing Schematic

Notes:

- Dose reduction is allowed at any time for reasons of safety or tolerability; during unscheduled or scheduled visits.
- During the Double-Blind Period, up-titration to a prior dose level is allowed at Investigator's discretion and only during a scheduled visit.
- At Visit 5 (Week 3), the dose should be up titrated to 50mg/day. In the event of tolerability/safety concerns, the dose may remain at 25 mg/day with Medical Monitor approval.
- Visit 6 (Week 5) is the last visit where up-titration can occur during the Double-Blind Period.

Open-label Extension Period:

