A minimum of 7 days is required between dose increases. Dose decreases may be made at any time, at the Investigator's discretion, for reasons of safety or tolerability. If, in the judgment of the investigator, the subject does not tolerate the minimum required dose (25 mg/day), the subject will be discontinued from the study.

During the OL extension treatment period, subjects will return to the clinic and have assessments as described in Table 3.

Telephone calls to the subjects will be made on the first 2 days after a dose adjustment (increase or decrease). At Study Week 12 and Study Week 16 (midpoint between Visit 11 and Visit 12, and midpoint between Visit 12 and Visit 13) the site staff will contact the subject via telephone in order to monitor for AEs, SAEs, and concomitant medications, as well as to remind subjects about adherence to study drug administration, and upcoming visits. If necessary, an unscheduled visit will be made as early as possible for dose adjustments or evaluation of safety/tolerability issues.

Follow-up Period (7 days):

All subjects who either complete the treatment period or discontinue early will have a follow-up visit for final safety assessments 7 days (\pm 2 days) after the last dose of study drug.

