7.3.2. Rationale for the Dosages

In the present study, flexible doses of SEP-363856 at 25, 50, or 75 mg/day will be investigated. Selection of this dose range was guided by the following:

- Maximum tolerated dose (MTD) determined for single doses of SEP-363856 administered to healthy adult male subjects in Study SEP361-101 (50 mg)
- Doses administered to healthy adult male subjects (Studies SEP361-103 and SEP361-104) in which SEP-363856 was found to have robust CNS activity (50 mg)
- Study SEP361-104 functional magnetic resonance imaging (fMRI) study in healthy male and female subjects with high or low schizotype characteristics demonstrating effects of SEP-363856 (50 mg) in brain regions such as the orbito-frontal cortex, insula and striatum
- Study SEP361-108 in patients with narcolepsy-cataplexy, suppression of REM sleep at 25 and 50 mg QD demonstrating CNS activity

• In the open-label study SEP361-106 (Part 2) that investigated the PK and efficacy of SEP-363856 at 75 mg/day for 28 days in male and female subjects with schizophrenia, improvement in efficacy measures (PANSS total score, CGI-S) compared with Baseline

Dose selection is further supported by acceptable safety and tolerability data from the 7-day (10 - 75 mg, QD) and open-label 28-day (75 mg, QD) in patients with schizophrenia. Phase 1 studies have also demonstrated dose-proportional increases in plasma SEP-363856 exposure (C_{max}) and AUC).

SEP-363856 has not been administered in patients with PD or PDP prior to this study. The study will therefore start at the lowest dose that showed CNS activity (25 mg).

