10.1.1. Dosage Adjustment Criteria

During the DB treatment period:

Subjects randomized to SEP-363856 will receive flexible doses of SEP-363856 (25, 50, or 75 mg/day). Subjects will receive SEP-363856 25 mg/day for 1 week (Days 1 - 7). If there are no safety or tolerability issues, subjects should be up-titrated to 50 mg/day. Subjects still receiving SEP-363856 25 mg/day must have their dose up-titrated to 50 mg/day at Visit 5 (Week 3). At the investigator's discretion, subject may up-titrate to 75 mg during scheduled visits. Up-titration will not be allowed after Visit 6 (Week 5). Dose reductions will be allowed by 1 dose level, at any time for reasons of safety and tolerability. Following a dose reduction, subjects may increase their dose to the next dose level up to Visit 6 (Week 5) at the Investigator's discretion and only during scheduled visits. If safety or tolerability issues result in study medication dose discontinuation or reduction, the Investigator must contact the medical monitor before the subject is re-challenged. The study medication can be re-introduced if agreed on by the Investigator and Medical Monitor.

Subjects randomized to placebo will receive placebo treatment throughout the study.

During the OL extension treatment period:

Subjects will receive flexible doses of SEP-363856 (25, 50, or 75 mg/day). Subjects will receive SEP-363856 25 mg/day for 1 week. If there are no safety or tolerability issues, subjects should be up-titrated to 50 mg/day at Visit 8 (OL Week 2; OL Day 8). Subjects still receiving SEP-363856 25 mg/day must have their dose up-titrated to 50 mg/day at Visit 9 (OL Week 3). At the investigator's discretion, subject may up-titrate to 75 mg during scheduled visits. Dose reductions will be allowed by 1 dose level, at any time for reasons of safety and tolerability. Following a dose reduction, subjects may increase their dose at the Investigator's discretion and

only during scheduled visits. If safety or tolerability issues result in study medication dose discontinuation or reduction, the Investigator must contact the medical monitor before the subject is re-challenged. The study medication can be re-introduced if agreed on by the Investigator and Medical Monitor.

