- Blood samples for clinical laboratory evaluation (hematology, serum chemistry, serum prolactin, HbA_{1c}, glucose panel, and lipid panel)
- Perform breath alcohol test
- If subject and caregiver signed separate genetic informed consent, collect blood samples for pharmacogenomics (CYPP450 2D6)
- Urine sample for urinalysis
- Blood sample for determination of plasma SEP-363856 and SEP-363854 (predose, and 1 sample between 1-3 hours post dose)
- SAPS-PD
- NPI
- CGI-S
- MMSE

- UPDRS II and UPDRS III
- SCOPA-DS
- SCOPA-NS
- RBDQ
- C-SSRS
- Adverse events
- Review randomization criteria
- Randomize to treatment
- Dispense study drug
- Administer first study drug dose

After receiving the initial dose, subjects will remain in the clinic for at least 2 hours of clinical observation, which will include periodic assessments of orthostatic vital signs (1 hour [\pm 15 min] and 2 hours [\pm 15 min] post dose); additional medical assessments can be performed as needed per investigator discretion. Findings will be collected on appropriate case report forms (CRFs). Subjects will be discharged home if medically stable. Telephone calls to the subjects will be made on the first 2 days following the visit (see Section 11.9.11).

If subject appears to be symptomatic as assessed by the site during a telephone contact and requires additional assessments in-clinic, an unscheduled visit will be made as early as possible (see Section 11.9.12).

11.9.3. Visit 4 (Day 8 ± 2 days), Visit 5 (Day 15 ± 2 days), and Visit 6 (Day 29 ± 2 days)

The following procedures will be conducted during each visit (unless otherwise specified):

- Prior/concomitant medications
- Study drug accountability
- Dispense study drug
- Vital sign measurements (including orthostatic effects)
- SAPS-PD
- NPI (Visit 5 only)
- CGI-S (Visit 5 only)
- MMSE (Visit 5 only)
- UPDRS II and UPDRS III
- SCOPA-DS (Visit 5 only)
- SCOPA-NS (Visit 5, only)
- RBDQ (Visit 5, only)

- C-SSRS
- Adverse events

If the subject titrates up, the subject will remain in the clinic for at least 2 hours of clinical observation, which will include periodic assessments of orthostatic vital signs (1 hour [\pm 15 min] and 2 hours [\pm 15 min] post dose); additional medical assessments can be performed as needed per investigator discretion.

Telephone calls to the subjects will be made on the first 2 days after a dose adjustment (increase or decrease) (see Section 11.9.11).

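### The 7-day minimum between dose increases is written only under the open-label heading, so the double-blind text and visit windows leave room for 75 mg three days after 50 mg

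*Protocol*

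**What the plan says.** **Double-blind dosing.** Protocol Section 7.1 states "Subjects will receive SEP-363856 25 mg/day for 1 week (Days 1 - 7". A subject with no safety or tolerability problem should then move to 50 mg/day at Visit 4. A subject still on 25 mg must move at Visit 5 unless the Medical Monitor agrees otherwise. For the top dose, the double-blind part of Section 10.1.1 says "At the investigator's discretion, subject may up-titrate to 75 mg during scheduled visits". The notes printed with Figure 2 add "Visit 6 (Week 5) is the last visit where up-titration can occur during the Double-Blind Period". The synopsis carries the same rules. None of this text gives a minimum interval between increases.

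**The interval rule.** "A minimum of 7 days is required between dose increases" appears in the synopsis and in Section 7.1, both times after the open-label heading. Section 10.1.1 sets out dose adjustment for both periods and omits it from both. Its open-label part repeats the individual steps, for example "Subjects still receiving SEP-363856 25 mg/day must have their dose up-titrated to 50 mg/day at Visit 9 (OL Week 3", but not the interval.

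**Visit timing.** The heading of Section 11.9.3 gives "Visit 4 (Day 8 ± 2 days), Visit 5 (Day 15 ± 2 days), and Visit 6 (Day 29 ± 2 days". The synopsis fixes the anchor: "All post-Baseline clinic visits will have a window of ± 2 days relative to the date of the Baseline visit (Visit 3". Section 7.1 has the higher dose taken in clinic on the day of an up-titration visit.

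**The concern.** The sponsor wrote a 7-day minimum between increases but placed it where it governs only the second part of the study. By then, about 24 of the 36 subjects will already have been randomized to active drug. Because each visit is timed from Baseline and not from the previous increase, a late Visit 4 followed by an early Visit 5 shortens the time at 50 mg with both visits in window.

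The double-blind period is where a titration rule matters most. Section 7.3.2 states: "SEP-363856 has not been administered in patients with PD or PDP prior to this study". Section 7.3.1 says there are no data in patients aged 65 or over. Section 7.3.2 gives 50 mg as the single-dose maximum tolerated dose in healthy men, and Section 4.3 reports one serious hypotension event in a healthy volunteer. SAP Section 4.1 plans no data monitoring committee. SAP Section 16.1.1 presents adverse events by dose at onset, and that attribution is weaker when a subject has spent only three days at a dose.

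**Working it through.** **Inputs** (Protocol Sections 7.1 and 11.9.3)

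- Visit 4: Day 8 ± 2, so Days 6-10
- Visit 5: Day 15 ± 2, so Days 13-17
- Visit 6: Day 29 ± 2, so Days 27-31
- The new dose starts on the visit day, so the days at a dose equal the later visit day minus the earlier one.

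**Nominal schedule.** 15 − 8 = 7 days. The planned days meet the 7-day rule exactly, with no slack for a late Visit 4 or an early Visit 5.

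**50 mg step: Visit 5 day minus Visit 4 day, all 25 in-window pairs**

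| Visit 4 day | Range of gaps to Visit 5 (days) | Pairs under 7 days |
|---|---|---|
| 6 | 7-11 | 0 of 5 |
| 7 | 6-10 | 1 of 5 |
| 8 | 5-9 | 2 of 5 |
| 9 | 4-8 | 3 of 5 |
| 10 | 3-7 | 4 of 5 |

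Total: 0 + 1 + 2 + 3 + 4 = 10 of 25. By length these are one pair at 3 days, two at 4, three at 5 and four at 6. Seven of the ten therefore miss by only 1 or 2 days. The shortest is Day 13 − Day 10 = 3 days.

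**Later steps.** Visit 5 to Visit 6 runs from 27 − 17 = 10 to 31 − 13 = 18 days, never under 7. In the double-blind period the gap between consecutive increases is confined to the Visit 4/Visit 5 pair.

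**25 mg step.** Doses before Visit 4 = Visit 4 day − 1. For Days 6 to 10 this gives 5, 6, 7, 8 and 9. On Days 6 and 7 the visit at which 50 mg is due falls inside the week assigned to 25 mg. This follows from the window alone. The move from 25 to 50 mg is the first increase, so a rule about time between increases would not reach it.

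**Does the proposed spacing fit?** Visit 4 on Days 8-10 plus 7 days gives Days 15-17, inside the existing Visit 5 window. The usable Visit 5 days are 15-17 after Day 8, 16-17 after Day 9, and Day 17 only after Day 10. That is six pairs, with gaps of 7 to 9 days.

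**Cost of a missed interval.** Counting doses to Day 42, 75 mg from nominal Day 15 gives 28 doses. If it waits for Visit 6 it gives 16 (from Day 27) down to 12 (from Day 31).

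**The case against.** The best reply is that the 7-day sentence names no period. Its paragraph also covers dose decreases and the rule for a subject who cannot tolerate 25 mg, and the next paragraph returns explicitly to the open-label period. A site could fairly take the sentence as study-wide. That stands as a reading, but the heading above it favours the narrower one, and Section 10.1.1 does not settle the matter. A reader might infer that the sponsor meant to allow faster escalation in the double-blind period. The documents do not support that; they show an ambiguity of placement. The drawing in Figure 2 is not shown and might give an interval. The logic by which the interactive response system assigns blister cards (Section 9.4) is not in the documents either.

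A reader might also infer that the missing rule permits 50 mg on Day 6 or 7. It does not. The dosing sentence assigns 25 mg through Day 7, and the protocol defines a week as 7 days (Table 5, Section 11). The window and the dosing sentence conflict, and nothing says which prevails.

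The third inference would be that short intervals are unsafe. This is not shown. The readable text gives no half-life. Section 7.3.2 reports acceptable tolerability at 75 mg/day in schizophrenia. Section 4.3 describes the hypotension events as transient, mild or moderate, and mostly needing no intervention. The single-dose tolerated maximum bears on the size of the dose more than on the interval. Two-hour observation with orthostatic vital signs, telephone calls on the next two days, and dose reduction at any time all limit acute risk. Rechallenge after a safety-related reduction requires contact with the Medical Monitor.

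**Conclusion.** The point holds as a modest safety correction. The double-blind dosing text and Section 10.1.1 lack the 7-day minimum, and the windows let 75 mg follow 50 mg after as little as 3 days. Separately, the Visit 4 window conflicts with a full week at 25 mg.

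The 10 of 25 pairs under 7 days should not be read as 40% of subjects. They count possible calendar combinations, carry no weights for how sites actually book visits, and matter only when the investigator chooses 75 mg at Visit 5. The 3-day case is one pair of the 25.

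The conclusion assumes that the unseen schematic adds no interval and that sites work from the written double-blind text. If the sponsor always meant the rule to be study-wide, the correction only says so.

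**What to change.** In the double-blind text of the synopsis and Section 7.1, and in Section 10.1.1, state: *At least 7 days at the current dose are required before any dose increase, in either period, including the first 25 mg step.* In Section 11.9.3, instruct sites to book Visit 4 on Days 8-10 and Visit 5 at least 7 days after Visit 4. State that a subject seen too early keeps the current dose until the next scheduled visit. The ± 2-day windows can stay as they are.

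**Cost**

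- Scheduling is slightly tighter, most of all after a Day 10 Visit 4, when Visit 5 must be on Day 17.
- An occasional subject seen too early at Visit 5 waits until Visit 6 for 75 mg, with 12-16 doses at that level by Day 42 instead of 28.
- A subject seen on Day 6 or 7 stays on 25 mg until Visit 5. In the open-label period, one seen at Visit 8 on OL Day 6 or 7 stays on 25 mg until Visit 9.
- A subject whose dose is reduced less than 7 days before Visit 6 could not go back up in the double-blind period.
- Supply is unaffected at this step: the longest booked gap between Visits 4 and 5 is 17 − 8 = 9 days, one 9-capsule card (Section 9.2.1).
- The SAP needs no change, since its Section 6.5 analyses data by the visit recorded on the case report form.

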7.1.1. Study Assessments

Double Blind Period:

Efficacy will be assessed by the SAPS-PD, the NPI, CGI-S, and the MMSE. Safety and tolerability will be monitored throughout the study by collection of AEs, clinical laboratory parameters, ECGs, vital signs, PE and NE, C-SSRS, body weight, and BMI. Subjects who have significant findings for suicidal ideation upon completion of the C-SSRS at any time during the study must be referred to the investigator for follow-up evaluation.

The quality of nighttime sleep as well as daytime sleepiness will be assessed by the SCOPA-NS and the SCOPA-DS, respectively. The effects of SEP-363856 on motor symptoms will be

assessed by the UPDRS II and III, and its effects on REM behavioral disorder assessed by the RBDQ.

Blood samples for the determination of SEP-363856 and SEP-363854 plasma concentrations will be collected as described in Table 2. Population pharmacokinetic (POPPK) analyses will be performed utilizing the data, results of which will be provided in a separate report.

OL Extension Period:

Safety and tolerability will be monitored throughout the OL Extension Period by collection of AEs, clinical laboratory parameters, ECGs, vital signs, PE and NE, C-SSRS, body weight, and BMI. Subjects who have significant findings for suicidal ideation upon completion of the C-SSRS at any time during the study must be referred to the investigator for follow-up evaluation.

Efficacy will be assessed by the NPI, the CGI-S, and the MMSE.

The quality of nighttime sleep as well as daytime sleepiness will be assessed by the SCOPA-NS and the SCOPA-DS, respectively. The effects of SEP-363856 on motor symptoms will be assessed by the UPDRS II and III, and its effects on REM behavioral disorder assessed by the RBDQ.

Blood samples for the determination of SEP-363856 and SEP-363854 plasma concentrations will be collected as described in Table 3. Population pharmacokinetic (POPPK) analyses will be performed utilizing the data, results of which will be provided in a separate report.

7.2. Treatment Assignment and Blinding

7.2.1. Treatment Assignment

The randomization schedule will be generated by a non-study biostatistician. Once a subject is deemed eligible to be randomized at Day 1 (Visit 3), the IXRS will perform treatment assignment. Subjects will be randomized to one of the following treatment groups for the double-blind treatment period in a 2:1 ratio (SEP-363856:placebo):

- SEP-363856 (25, 50 or 75 mg/day flexible dosing QD for 6 weeks)
- Placebo (QD for 6 weeks)

Once a randomization number has been assigned, it cannot be reused.

7.2.2. Blinding

During the Double-blind Treatment Period, subjects, Investigator staff, persons performing the assessments, clinical operations personnel, data analysts, and personnel at central laboratories will remain blind to the identity of the treatment from the time of randomization until database lock and unblinding, using the following methods; (1) randomization data are kept strictly confidential until the time of unblinding, and will not be accessible by anyone else involved in the study with the exception of bioanalytical personnel involved in the analysis of PK samples; (2) the identity of the treatments will be concealed by the use of study drugs that are all identical in packaging, labeling, schedule of administration and appearance.

Actual subject identity for plasma concentrations of SEP-363856 and SEP-363854 will not be disclosed before the database lock and the unblinding of the double-blind treatment.

After completion of the DB treatment period, all subjects will receive unblinded flexibly dosed SEP-363856.

